then crossed over.^[20] Children in the intervention group practised active trunk movements through a purposely built force platform connected to computer games in sitting for 3 months (no intervention dosage provided). Significant differences were found in the shoulder girdle position and spinal profile and significant increase in the overall scores at rest (specifically associated postural reaction) and during reaching (specifically the proximal stability rating) according to the SACND after intervention.^[20] The Nintendo Wii Fit was used again in a repeated-measure multiple single-subject study conducted by Jelsma and colleagues (2013).^[17] A group of 14 children with hemiplegia CP of GMFCS levels I and II were randomly allocated to start the intervention first or 2 weeks later. During the intervention, the children received training using the console, four times a week for 25 minutes per session for three weeks. Significant improvement in balance, as measured with the modified Bruininks-Osteretsky Test of Motor Proficiency Version 2 (BOT2), was found immediately and 2-month post-intervention but no changes were found in the running, agility and speed in the BOT2 and Timed up and downstairs.^[17] However, in a small RCT, 18 children with CP of GMFCS levels I or II were randomised into an intervention group and a control group and then crossed over after five weeks.^[18] The children received practice on the Nintendo Wii Fit Balance games at least 30 minutes, five days a week during the intervention period. No significant difference was found in the change of centre of pressure during the modified Sensory Organization Test, in the muscle responses after perturbations and in the control of anterior-posterior and medial-lateral directions in the rhythmic weight shift test between the intervention and control groups.^[18] In summary, promising though conflicting results were found among these studies whether ICP is effective in improving trunk control in children with CP. The main limitations of these studies are the overall low levels of study quality, small sample sizes and heterogeneous population groups under the umbrella term CP. In fact, similar conclusions for future studies with larger sample sizes and rigorous study designs have been echoed from four recent systematic reviews on the topic.^[11-14]

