- (4) Able to follow instructions to interact in simple computer games

Sample size calculation: There is no previous published study using the primary outcome measure (see below under Methods) to examine the effect of the ICP on trunk control in this population group, hence, no sample size calculation is possible based on previous data. Thus it is estimated that 20 children with 10 children in each arm for this pilot RCT is appropriate and feasible. The sample size will be the largest among the previous studies in this area.

Exclusion criteria:

- (1) Children with epilepsy/ seizures that could be elicited by flashing lights or sudden loud noises from computer screens

(ii) Methods

Outcome measures (OM) used in this proposal include:

Primary study outcome:

- (1) Segmental Assessment on Trunk control (SATCo)^[8] assessment on the child's segmental trunk control by progressively reducing the trunk support from the shoulder girdle to assess the

head control, through support at the axillae (upper thoracic), inferior scapula (mid-thoracic), lower ribs (lower thoracic), below ribs (upper lumbar), pelvis (lower lumbar) and no support to measure full trunk control.^[8] The trunk control is tested under 3 different conditions in sitting: to maintain the posture (static control), during voluntary head movements (active control) and recovery of trunk control after a disturbance of balance by a nudge (reactive control).^[8]

Secondary study outcomes:

(2) Pediatric Reach Test (PRT)^[22] assessment on balance in sitting and standing positions. The distance how far the child can reach forward, to right and to left will be measured in sitting and standing. High construct validity has been shown between the PRT in standing and a laboratory test of steadiness in quiet stance ($r= 0.79$) and age ($r= 0.83$) in a group of 19 typically developing children. High construct validity has also been shown between the total PRT score and GMFCS level ($r= 0.88$) among a sample of 10 children with cerebral palsy. Test-retest reliability and inter-tester reliability with children with cerebral palsy was moderate to high (intraclass correlation coefficients= 0.54 to 0.88 and 0.50 to 0.93 respectively)^[22] and

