(3) Gross Motor Function Measure 88 (GMFM 88)^[23] assessment on general gross motor function in various positions including lying, sitting, 4-point kneeling, high kneeling and standing. The intra- and inter-rater reliability of the GMFM 88 have been shown to be very high (ICC= 0.99 in both cases).^[23]

(4) 2-minute walk test^[24] distance covered in a period of 2 minutes with self-chosen comfortable speed will be measured. The walk test has been shown to have high test-retest, intra- and inter-rater reliability.^[24]

(5) The height and weight of the children

(iii) Study design

20 children with CP or similar physical disabilities will be recruited from 2 special schools for children with physical disabilities in Hong Kong for this pilot RCT (see 'Existing facilities' for details). Informed consent will be sought from the parents or guardians before the study will commence. After the initial assessment, all study children will be randomly allocated into a control group or treatment group (10 children in each arm) using a 'draw card from the hat'. The randomization will be separately done in each school so as to take into account the heterogeneity of the children and treatment regime in each school. The children in the treatment group will receive training on their trunk control using the Tymo in sitting 4 times per week for 20 minutes per session. The treatment will last for 6 weeks. All study children will continue their usual therapies at school but will be asked to stop playing any interactive computer play, which is designed to train balance such as Nintendo Wii balance board, during the study period. As there is no strong research evidence that commercial computer games are effective in improving the balance for children with CP and this type of commercial computer play is not a routine training exercises for balance in the treatment sessions at the schools, it is believed that discontinuing this type of 'training' for 6 weeks would not cause detrimental effect on the balance of the study children.

All the assessment will be carried out by a blinded assessor (PA), who is not aware of the group allocation of the children. All the children will be assessed at the beginning, and 3, 6 and 12 weeks after the commencement of the intervention. The last assessment aims to examine the medium-term effect on their trunk control post-intervention.

Intervention:

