All participating children will be calibrated using the Tymo in a static sitting position in each treatment session by the research staff. Force and weight distribution will be calibrated by asking the child to move the trunk forward, backward and sideways as far as s/he can. The amplitude of the force and weight distribution between the two sides of the body will be recorded. These

information will be used to set up the Tymo as a balance training module (the intervention) by the software, in which the child will move the trunk forward, backward and sideways to participate in a computer game in a sitting position (Tables 1 and 2). The child will be allowed to choose which game they want in each treatment session and they have to stay on the same game for at least 10 minutes before changing to another game. In other words, the child will have a maximal choice of 2 computer games in each treatment session. All children will start at a medium level of difficulty. Only if the child is unable to score any point in 3 trials in a row, the difficulty level will be reduced to one level down. Similarly, if the child scores full points in 3 trials in a row, the difficulty level will be increased to one level up. The progression of the intervention will then be closely monitored by the research staff. A logbook will be used for each child to record the level of difficulty in each treatment session, the number of treatment sessions, duration of each session and general comments on the child in each session during the intervention phase. The intervention will be supervised by a research assistant, who will be employed for the study.

(iv) Data processing and analysis

Statistical analyses: SPSS for Windows (version 20) will be used to analyse the results. Mann Whitney U test will be used to compare the results of the OM(1) between the intervention and control groups and independent t-test for OM(2) to OM(5). The statistical significance level is set at $p < 0.05$.

[Word Court: 3814]

e) Existing Facilities:

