Both the PA and co-applicant are very experienced paediatric physiotherapists with over 20 years of experience in managing young children with movement disorders. The mother institution of the PA is the only University in Hong Kong running the undergraduate degree in Physiotherapy and the Department of Rehabilitation Sciences at the Hong Kong Polytechnic University has abundant experiences in conducting research studies on individuals with movement disorders. Space will be provided for data storage (both hard and soft data) and statistical software will be provided for the present study. The co-applicant is the developer of the SATCo and is active in conducting research studies with collaborating researchers in USA and Denmark in examining trunk control in children with CP.

The Medical Technologies Ltd is the sole agent in Asia, which manages the Tymo Therapy plate. The agent will provide training and support in using the Tymo Therapy plate to all relevant personnel in this study in Hong Kong, as part of their quote on the equipment.

Initial contact has been made with the physiotherapists in-charge at 3 special schools in Hong Kong, namely the John F Kennedy Centre, the Red Cross Princess Alexandra School and Pui Oi School (all are special schools for children with physical disabilities), who all show interests to participate in the study. Specifically, the study children will be recruited from the first two schools and these schools will accommodate the Tymo Therapy Plate on site during the intervention phase. The physiotherapists in-charge tentatively believed that recruitment of 20 children with CP or similar physical disabilities is feasible in the first 2 schools. In case the recruitment falls short or a substantial drop-outs during the study period, Pui Oi School would be approached for further recruitment.

f) Justification of Requirements:

Staffing- a Physiotherapist will be employed to supervise the children to carry out the ICP at respective schools. Salary for this personnel is set as point 19 (median point of Physiotherapist II) of MPS, i.e. \$32,560 per month + \$1,500 MPF per month for 6 months= \$204,360 because the personnel is required to have experience in managing paediatric clients with physical disabilities and has

understanding of postural control in children.

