Equipment- hiring Tymo Therapy plate and associated equipment= \$61,405. The Medical Technologies Ltd is the sole agent in Asia, which manages the Tymo Therapy plate and this is the only equipment, as far as the PA knows, that provides this type of training on trunk control using the concept of ICP. The quote provided by the agent includes assembling, transporting and disassembling the equipment across the 2 special schools.

Travel cost for intervention= \$100 per returned trip X 5 days X 16 weeks = \$8,000

Travel cost for blinded assessments= \$100 per returned trip X 4 assessments per child X 10 trips (assessing 2 children per day)= \$4,000

Gifts to participating children= \$20 X 20 children = \$400

External hard drive for data storage= \$500

Total= \$278,665

g) Purpose and Potential:

Cerebral palsy (CP) is the most common physical disability in childhood, affecting about 1.3 per 1000 live-births in Hong Kong. Regardless the severities of the disability, children with CP have inadequate control in their trunk, affecting their balance in maintaining their posture in sitting and standing positions and regaining their balance if challenged in both positions. With the advance in computing technology, interactive computer play (ICP) has become popular in rehabilitation for people with motor impairments, including children with CP. During an ICP, a child interacts and plays with virtual objects in a computer-generated environment, through the use of a computer console or platform and the software, allowing the child to control the games through certain body movements. Because the computer games are fun and enjoyable, the child will continuously repeat the required body movements so as to get a high score in the game without losing the interest. The numerous repetitions and feedback from the game scores fulfil the principles of motor learning. Hence, ICP may be a feasible way to improve trunk control in children with CP, in addition to the conventional therapies. Up to date, there is controversial evidence in using ICP or virtual reality in improving balance in children with CP. The main reasons for inconclusive effectiveness of ICP in improving trunk control on this population group include low quality of research study designs, small sample sizes and insensitive outcome measures. In addition, use of commercial ICP may not be able to specifically train the trunk control and translate the improvement in the trunk control into the game scores.

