The present study is designed to overcome these shortfalls. It is a single blinded controlled trial with 20 children with CP in each arm. The intervention, ICP is a specifically designed balance training tool for rehabilitation (www.tyromotion.com). One of the outcome measures used is an assessment of segmental trunk control, which will capture subtle changes in trunk control in different segments, instead of considering the whole trunk as one unit. The targeted children with CP are relatively homogeneous. It is the first of the series in using ICP for children with movement disorders. If the intervention is proven to be effective, ICP may be an adjunct to the conventional Physiotherapy to children with movement disorders. With the future Hong Kong Children's Hospital in mind, the ICP may be an essential piece of equipment in the rehabilitation program in the wards. Furthermore, future studies on different population groups with movement disorders, such as Developmental Coordination Disorders and children with preterm birth, will be conducted using the ICP.

Results of the present study will be presented in local and overseas conferences, e.g. Hong Kong Physiotherapy Association conference, American Academy of Cerebral Palsy and Developmental Medicine conference etc. Results will also be submitted for publication in high ranking journals such as Developmental Medicine and Child Neurology (impact factor 3.292) and Journal of Physiotherapy

(impact factor 2.894).

h) Key References:

1. Oskoui, M., et al., *An update on the prevalence of cerebral palsy: a systematic review and meta-analysis*. *Developmental Medicine and Child Neurology*, 2013. **55**(6): p. 509-519.
2. Yam, W., et al., *Prevalence study of cerebral palsy in Hong Kong children*. *Hong Kong Medical Journal*, 2006. **12**(3): p. 180-184.
3. Mutch, L., et al., *Cerebral palsy epidemiology: where are we now and where are we going?* *Developmental Medicine & Child Neurology*, 1992. **34**: p. 547-551.
4. Palisano, R.J., et al., *Development and reliability of a system to classify gross motor function in children with cerebral palsy*. *Developmental Medicine & Child Neurology*, 1997. **39**: p. 214–23.
5. Carlberg, E.B. and M. Hadders-Algra, *Postural control in sitting children with cerebral palsy*, in *Postural Control: a Key Issue in Developmental Disorders*, M. Hadders-Algra and E.B. Carlberg, Editors. 2008, Mac Keith: London. p. 74-96.

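### The plan says it overcomes the small samples of earlier studies, but with 10 children per arm and tests only it is set up for a significance verdict that it is too small to give

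*Combined protocol and SAP*

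**What the plan says.** Section g) Purpose and Potential attributes the inconclusive evidence on interactive computer play to "low quality of research study designs, small sample sizes and insensitive outcome measures". It continues: "The present study is designed to overcome these shortfalls". The next sentence gives the size of this trial as twenty children per arm. The same paragraph looks ahead to use alongside conventional physiotherapy and in a future children's hospital, introduced by "If the intervention is proven to be effective".

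The other sections give half that number. The sample size paragraph in d)(i) says that no calculation can be based on previous data and concludes: "Thus it is estimated that 20 children with 10 children in each arm for this pilot RCT is appropriate and feasible". Section d)(iii) repeats 10 per arm, and section e) reports the schools' view that "recruitment of 20 children with CP or similar physical disabilities is feasible in the first 2 schools". The budget in section f) allows for 20 gifts.

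The statistical plan in d)(iv) is short. SATCo, the primary outcome, is compared by a Mann-Whitney U test, and outcomes (2) to (5) by independent t-tests. "The statistical significance level is set at" p < 0.05. No effect estimate, confidence interval or SD is listed as an output. The hypotheses in section c) are also worded as significant improvement after six weeks.

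**The concern.** The plan names small samples as a reason why earlier work could not settle the question and says that this trial removes that weakness. At 10 per arm it does not, and the conflicting figure of 20 per arm in section g) makes the claim look better supported than it is.

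This matters because the planned output is a verdict at p < 0.05. At this size a non-significant result is likely even if the benefit is sizeable, and a significant one tends to exaggerate the effect. Without an interval the reader cannot see how little either result excludes. The trial calls itself a pilot and the first of a series, so its most useful products are an estimate, its uncertainty, the SD and the drop-out rate. The analysis section promises none of these.

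**Working it through.** **The stated number.** The figure of 20 cannot be reproduced, because d)(i) gives no effect size, SD or power. What can be computed is what the stated number is able to detect or estimate. That needs no earlier data if effects are expressed in SD units.

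**Which number.** Ten per arm is stated in d)(i) and d)(iii). Section e) has 20 in total and section f) budgets for 20 children. Only section g) has 20 per arm. Ten per arm is therefore taken as intended, and 20 per arm is shown for comparison.

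**Size against earlier studies.** The background describes studies of 6, 1, 16, 13, 14 and 18 children. The margin over the largest is 20 − 18 = 2 children. The text leaves slightly unclear whether 16 is a study total or one group.

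**Inputs.** n per arm = 10 (or 20); alpha = 0.05 from d)(iv), taken as two-sided because the plan does not say; effect d in SD units of whatever is compared, over an assumed range of 0.5 to 1.4; normal data, equal SDs, no drop-out.

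**t-test power.** Noncentral t with 2n − 2 degrees of freedom and noncentrality d × √(n/2). For n = 10 the critical value is t(18) = 2.101 and √(10/2) = 2.236. For d = 0.8 the noncentrality is 0.8 × 2.236 = 1.79, and power is 40%.

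| Quantity | 10 per arm | 20 per arm |
|---|---|---|
| Power at 0.5 SD | 18% | 34% |
| Power at 0.8 SD | 40% | 69% |
| Power at 1.0 SD | 56% | 87% |
| Effect detectable with 80% power | 1.32 SD | 0.91 SD |
| Expected 95% CI half-width | 0.94 SD | 0.64 SD |

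**Interval half-width.** t × √(2/n). For n = 10: 2.101 × √0.2 = 2.101 × 0.447 = 0.94 SD. For n = 20: 2.024 × √0.1 = 2.024 × 0.316 = 0.64 SD.

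**Primary test.** SATCo is compared by Mann-Whitney, so the t-test figures are slightly optimistic for it. Simulation with 10 per arm and normal data (4,000 runs per point) gives about 15% power at 0.5 SD, 35% at 0.8 SD, 51% at 1.0 SD and 73% at 1.3 SD. At 1.32 SD power is about 76%. It reaches 80% near 1.4 SD (81% on continuous data, 78% on a version rounded to mimic an ordinal scale).

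**Drop-out.** The plan gives no rate. If 8 per arm remained (20% loss, assumed), t-test power at 0.8 SD would be 32% and the detectable effect 1.51 SD.

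**Exaggeration.** In simulated t-tests with 10 per arm, significant results overstate a true effect of 0.5 SD about 2.2-fold on average, and one of 0.8 SD about 1.5-fold.

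**The case against.** The strongest reply is that this is a pilot, so labelled in c), d)(i) and d)(iii), and that 20 children is a reasonable number for one. That stands, and nothing here argues for more children. The d)(i) statement is also narrower than a claim that no calculation of any kind is possible: it refers to calculation from previous data, which is fair. A precision statement would add to it, not contradict it.

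The shortfalls in section g) include study quality and insensitive outcomes, which the plan does address through randomisation, a blinded assessor and SATCo. That stands too, so only the sample-size part of the claim fails. The word proven is conditional and sits in a section about purpose. This softens it, but the paragraph still ties the result to clinical adoption.

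Two stronger readings are tempting.

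- A reader might infer that this parallel trial is several times less precise than the 18-child RCT, whose children were "randomised into an intervention group and a control group and then crossed over after five weeks". Any such multiplier needs a within-child analysis, an assumed within-child correlation and no carry-over. The background states none of these. It describes that study's result as a comparison between groups, and in another study it reports a balance gain still present two months after training, which makes absence of carry-over doubtful. No ratio can be supported.
- A reader might infer that the analysis can produce nothing but p-values. For outcomes (2) to (5) a t-test is computed from group means and SDs, so estimates are available and merely unplanned. The gap is wider for SATCo, where a Mann-Whitney test gives no effect size without a further step.

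**Conclusion.** The concern holds for sample size and for the planned output. Section g) claims a property that the design does not have, and supports it with a per-arm number that conflicts with the rest of the document. At 10 per arm the trial reliably detects only very large effects: about 1.4 SD on the primary test and 1.32 SD on the t-tests. The interval would extend about 0.94 SD either side of the estimate. Reading section g) literally does not rescue the claim, since 20 per arm still falls short of 80% power at 0.8 SD.

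The figures assume a two-sided 5% level, normal data and complete follow-up. SD-unit results carry over only approximately to an ordinal measure such as SATCo. The plan names no meaningful difference, so the power values describe a range and not a target. The documents do not support the conclusion that 20 children is wrong for a pilot, or that the trial improves on nothing in earlier work.

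**What to change.** Keep 20 children, and change the following:

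1. In section g), correct the size to 10 per arm, in line with d)(i), d)(iii) and e).
2. In the same section, remove sample size from the shortfalls that the study claims to overcome, and replace the reference to proof with pilot wording, for example: if the pilot estimates support a larger trial.
3. In d)(i), add that 10 per arm gives 80% power for about 1.4 SD (Mann-Whitney, simulated on normal data) or 1.32 SD (t-test), with an expected 95% interval half-width of about 0.94 SD for a mean difference. Do not give 1.32 SD as the figure for the primary outcome.
4. In d)(iv), make the main result the between-group difference at week 6 with its 95% confidence interval: Hodges-Lehmann for SATCo, noting that ties will make it coarse, and the mean difference for outcomes (2) to (5). Week 6 matches the hypotheses in section c). The planned tests can stay alongside.
5. Report SDs and the drop-out rate for sizing the next trial.

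The cost is some rewording and a little extra output, with no added children, visits or procedures. The downside is that the stated promise of the study becomes less favourable.
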